### **7.1.3. Additional Safety Assessments**

Additional safety measures will be summarized for the Safety analysis set. Only data in the study eye will be presented in tabulations. Data may be tabulated by visit and/or for the overall study (i.e. subjects with at least one finding during the study) as indicated. Summaries for the overall study will include data from unscheduled visits.

The criteria for clinical significance varies by measure.

#### **7.1.3.1. Corrected Visual Acuity**

The actual and change from baseline in BSCVA will be summarized by visit. The summary will include continuous descriptive statistics on the number of letters read correctly. In addition, the number and percentage of subjects with a decrease of greater than or equal to 15 letters (3 lines) will be summarized by visit.

A visual acuity subject listing will be provided for all visual acuity data including pinhole VA.

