## 1. Introduction

This statistical analysis plan (SAP) describes the statistical methods to analyze all safety data from protocol IDOS-106-EXCH. Any changes to this plan will be reflected as amendments before the database lock and/or documented in the clinical study report. One database lock will occur after all subjects have completed the Month 12 Post-Exchange (PE) visit or have exited the study prior to that time.

Specifications of tables, figures, and data listings are provided in another document.

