## 4. General Statistical Considerations

Demographic and safety data collected on the case report forms (CRFs) will be displayed in tabulations and data listings. Only data from scheduled visits will be used in tabulations unless otherwise specified. No formal statistical testing will be performed. All data summaries and statistical analyses will be performed using SAS® software, Version 9.4 or higher.

Continuous data will be summarized using the number of observations, mean, standard deviation, median, minimum, and maximum. Continuous data may also be dichotomized, or otherwise split, into clinically meaningful categories and may be further analyzed as categorical data as specified in the individual endpoints.

Categorical data will be summarized using frequency counts and percentages. Unless otherwise stated, subjects with missing visit data will be omitted from both the numerator and denominator of such calculations.

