#### **7.1.3.3. Lens Findings**

Lens measures are collected at Screening and each postoperative visit. Lens measures include lens status, posterior capsule opacification, nuclear lens opacity, cortical lens opacity, and posterior subcapsular lens opacity.

For each measure, the number and percentage of subjects will be summarized by visit for each severity grade/category.

[figure not shown]
All lens data will be listed by subject.

Other lens findings will be provided in a separate listing. Lens status (phakic or pseudophakic) will be listed and not tabulated.

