#### 7.1.3.8. Specular Microscopy

Specular microscopy findings are collected at the Screening, Month 3 PE, and Month 12 PE visits. Endothelial cell density (ECD), percent hexagonality, and the coefficient of variation (COV) will be assessed from calibrated specular microscope images. The actual, change from baseline, and percent change from baseline in ECD ( $\text{cells/mm}^2$ ) will be summarized as a continuous variable by visit for the central location. In addition, the number and percentage of subjects with central ECD loss will be tabulated by visit and for the overall study (i.e., based on the minimum change from baseline across all postoperative visits) for the following categories:

The actual and change from baseline in percent hexagonality (%) and COV (%) will be summarized continuously by visit for the central location.

A listing presenting all ECD data will be provided.

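### Loss of 15 or more letters is tabulated by visit only, so a loss measured only at an unscheduled visit enters no row and no ever-affected count is specified

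*SAP*

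**What the plan says.** Four places in the SAP govern this table.

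- SAP 4 sets the default: "Only data from scheduled visits will be used in tabulations unless otherwise specified".
- SAP 7.1.3 gives the exception for the additional safety measures: "Data may be tabulated by visit and/or for the overall study (i.e. subjects with at least one finding during the study) as indicated". It adds: "Summaries for the overall study will include data from unscheduled visits".
- SAP 7.1.3.1 chooses the form for visual acuity: "the number and percentage of subjects with a decrease of greater than or equal to 15 letters (3 lines) will be summarized by visit". It also promises that "A visual acuity subject listing will be provided for all visual acuity data including pinhole VA".
- SAP 7.1.3.8 tabulates categories of central ECD loss by visit and also "for the overall study (i.e., based on the minimum change from baseline across all postoperative visits)".

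Corrected visual acuity is one of the safety endpoints in SAP 2.2. SAP 1 notes that "Specifications of tables, figures, and data listings are provided in another document"; that document is not available here.

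**The concern.** The trial has a single objective, the safety of the exchange procedure, and no formal testing is planned. The descriptive counts are therefore the result. For a 3-line loss, the natural safety question is how many study eyes ever had one after the exchange. The table specified in SAP 7.1.3.1 cannot answer it, for two reasons.

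First, by-visit rows do not show whether the cases in successive rows are the same subjects or different ones.

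Second, a subject who comes in between visits with reduced vision is measured at an unscheduled visit, and the rules keep that measurement out of the table. If vision recovers before the next scheduled visit, or the subject exits or misses later visits, the loss appears in no row. SAP 4 also removes subjects with missing visit data from both numerator and denominator, so an affected subject who exits leaves no trace in later rows.

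**Working it through.** **Reading the rules together.** The plan states no figure on this point to reproduce, so the first step is textual.

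1. The default is scheduled visits only (SAP 4).
2. Unscheduled data enter through an overall-study summary, where one is indicated (SAP 7.1.3).
3. The visible text of SAP 7.1.3.1 indicates a by-visit summary and nothing else.
4. Hence a loss of at least 15 letters measured only at an unscheduled visit adds 0 to every row, and no ever-affected count is specified.
5. SAP 7.1.3.8 shows that the SAP names the overall form when it wants it. Visual acuity is not alone in lacking it, however. The visible lens text reads "For each measure, the number and percentage of subjects will be summarized by visit for each severity grade/category", the slit-lamp text is similar, and parts of both sections are not shown. ECD loss is the one overall summary visible in this copy.

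**What by-visit rows can tell a reader.** Inputs: N is about 45 (Protocol 6.1), taken as all evaluable. The number of rows k is an assumption, because the schedule of acuity measurements is not visible; there are at most six scheduled post-exchange visits. With row counts c1 to ck, the number of subjects ever affected at scheduled visits lies between max(c) and min(45, sum of c). With one case in each row, the lower bound is 1/45 = 2.2% and the upper bound is k/45:

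| Rows k | Largest row | Upper bound, ever affected |
|---|---|---|
| 2 | 1/45 = 2.2% | 2/45 = 4.4% |
| 3 | 1/45 = 2.2% | 3/45 = 6.7% |
| 4 | 1/45 = 2.2% | 4/45 = 8.9% |
| 5 | 1/45 = 2.2% | 5/45 = 11.1% |
| 6 | 1/45 = 2.2% | 6/45 = 13.3% |

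Losses measured only at unscheduled visits come on top. With one such subject and no others, every row shows 0/45, while an overall count would show 1/45 = 2.2% (exact 95% CI 0.1% to 11.8%). Each further such subject adds 2.2 percentage points to the true count and nothing to any row.

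**Room for unscheduled findings.** From the visit windows in Protocol 3:

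| Interval | Nominal gap (days) | Longest gap within windows (days) |
|---|---|---|
| Week 4 to Month 3 | 91 − 28 = 63 | 105 − 25 = 80 |
| Month 3 to Month 6 | 182 − 91 = 91 | 212 − 77 = 135 |
| Month 6 to Month 12 | 365 − 182 = 183 | 395 − 152 = 243 |

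**The case against.** The strongest reply is that the absence of an overall count is not proven. Table specifications sit in another document and may contain the row. This copy of the SAP also has gaps: the ECD loss categories, for example, are missing after the sentence that introduces them. That stands as a limit. It does not change what the visible rule says, and a count of this importance belongs in the SAP text in any case.

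A second reply is that the information is captured elsewhere. All acuity values are listed by subject, and with about 45 subjects a hand count is feasible. Protocol 9 treats any clinically significant change as an adverse event regardless of causality, Protocol 9.1 makes sight-threatening events serious, and the adverse event tables in SAP 7.1.2 count each subject once. This stands in part: the data are not lost. But a listing is not a count, and the adverse event tables do not apply the 15-letter threshold. Capture there is also uncertain, because another sentence in Protocol 9 limits recording to study-eye events judged related to the implant or procedure, and the serious definition turns on risk of permanent loss.

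Third, the size is hypothetical. No vision-loss rate is given, no visible text says that acuity is measured at unscheduled visits, and the upper bounds assume a different subject in every row. A lasting loss would be counted at the next scheduled visit attended. All of this is correct. The exposure is confined to losses that resolve, or that are followed by missed visits or early exit, and to the inability to link rows.

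**Conclusion.** The point holds for the visible text. SAP 4, 7.1.3 and 7.1.3.1 do not contradict each other, but together they leave a loss of at least 15 letters seen only at an unscheduled visit out of the table, and they specify no ever-affected count for a named safety endpoint in a safety-only trial.

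The size cannot be estimated from the documents. The figures above show how wide the ambiguity can be, and they rest on 45 evaluable subjects, one case per row and an assumed two to six rows. No test or estimate is invalidated. It is a change that should be made, held with medium confidence because the table specifications could not be seen.

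**What to change.** Add to SAP 7.1.3.1: *The number and percentage of subjects with a decrease from baseline of at least 15 letters at any post-exchange visit, including unscheduled visits, will be summarized for the overall study.* Use as denominator the safety-set subjects with at least one post-exchange BSCVA measurement, and keep the by-visit rows.

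Two optional additions are the number still affected at the last available visit and an exact 95% confidence interval.

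The cost is one sentence and one table row from data already collected and listed, with no new data and no more subjects. SAP 1 allows amendments before database lock. If the table specifications already contain the row, only the sentence is needed. The downside is that an any-visit count includes transient early post-operative loss and rises with how often a subject is examined. The retained by-visit rows and the optional last-visit count help a reader separate transient from lasting loss.

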#### **7.1.3.2. Slit Lamp Examinations**

Slit lamp measures collected on the CRF include corneal edema, corneal opacity, epithelium, endothelium, guttata, anterior chamber depth, anterior chamber cells, anterior chamber flare, pupil, iris, conjunctival hyperemia, and iris color change. All slit lamp measures, excluding conjunctival hyperemia and iris color change, are collected at Screening and each postoperative visit. Conjunctival hyperemia and iris color change are collected at all postoperative visit except for the Day 1 PE visit.

[figure not shown]
For each measure, the number and percentage of subjects will be summarized by visit for each severity grade/category.

Conjunctival hyperemia will be summarized by visit.

All slit lamp data will be listed by subject. An additional slit lamp listing for subjects with findings will be presented.

Other slit lamp findings will be provided in a separate listing.

[figure not shown]
#### **7.1.3.3. Lens Findings**

Lens measures are collected at Screening and each postoperative visit. Lens measures include lens status, posterior capsule opacification, nuclear lens opacity, cortical lens opacity, and posterior subcapsular lens opacity.

For each measure, the number and percentage of subjects will be summarized by visit for each severity grade/category.

[figure not shown]
All lens data will be listed by subject.

Other lens findings will be provided in a separate listing. Lens status (phakic or pseudophakic) will be listed and not tabulated.

#### **7.1.3.4. Ophthalmoscopy Examinations**

Dilated fundus assessments are evaluated at the Screening and Month 12 PE visits. Either undilated or dilated fundus assessments may be evaluated at the Week 4 PE, Month 3 PE, and Month 6 PE visits. Dilated and undilated fundus measures (Macula, Vessels, Periphery, Vitreous, Other) will be tabulated by visit for each severity grade.

[REDACTED]

Nerve abnormality findings are collected at the Screening, Week 4 PE, Month 3 PE, Month 6 PE, and Month 12 PE visits. The number and percentage of subjects with findings (Segmental Loss of Neuroretinal Rim, Nerve Fiber Layer Loss, Disc Hemorrhage, Other) will be tabulated by visit.

[REDACTED]

All nerve abnormality data will be listed by subject.

[REDACTED]

Vertical cup-to-disc ratio is evaluated at the Screening, Month 3 PE, and Month 12 PE visits. The actual and change from baseline in vertical cup-to-disc ratio will be summarized as a continuous variable by visit.

|| [REDACTED]

[REDACTED]

A listing of vertical cup-to-disc ratio and change in vertical cup-to-disc ratio will be provided by subject.

#### 7.1.3.5. Gonioscopy

Gonioscopy assessments are performed at the Screening, Week 4 PE, Month 3 PE, Month 6 PE and Month 12 PE visits. Gonioscopy findings include goniosynechiae, angle rubeosis, and other angle abnormalities.

#### 7.1.3.6. Implant Visibility

#### 7.1.3.7. Visual Field

Visual field mean deviation (MD) is collected at Screening and the Month 12 PE visit. The actual and change from baseline in visual field MD will be summarized as a continuous variable by visit.

A listing will be presented for all visual field MD data.

#### 7.1.3.8. Specular Microscopy

Specular microscopy findings are collected at the Screening, Month 3 PE, and Month 12 PE visits. Endothelial cell density (ECD), percent hexagonality, and the coefficient of variation (COV) will be assessed from calibrated specular microscope images. The actual, change from baseline, and percent change from baseline in ECD ( $\text{cells/mm}^2$ ) will be summarized as a continuous variable by visit for the central location. In addition, the number and percentage of subjects with central ECD loss will be tabulated by visit and for the overall study (i.e., based on the minimum change from baseline across all postoperative visits) for the following categories:

The actual and change from baseline in percent hexagonality (%) and COV (%) will be summarized continuously by visit for the central location.

A listing presenting all ECD data will be provided.

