6 METHODS

6.1 Subjects

Approximately 15 centers that enrolled subjects in the GC-009 clinical trial will participate in this study. Approximately 45 subjects who were previously implanted with the Travoprost Intraocular Implant in the GC-009 study (1st Cycle) will have their first implant exchanged with a second Travoprost Intraocular Implant (2nd Cycle). After signing informed consent, prospective subjects will be evaluated to determine whether they meet all other eligibility requirements at Visit 1 (Screening).

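### An eye with no gradable Month 12 specular image because of corneal failure leaves the Month 12 ECD-loss percentages, and in the overall row it is classified by an earlier value or dropped

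*SAP*

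**What the plan says.** SAP 7.1.3.8 (Specular Microscopy) sets the timing: "Specular microscopy findings are collected at the Screening, Month 3 PE, and Month 12 PE visits". ECD, hexagonality and coefficient of variation "will be assessed from calibrated specular microscope images", so an ECD value exists only where an image can be read. For the central location, "the number and percentage of subjects with central ECD loss will be tabulated by visit and for the overall study". The overall row is "based on the minimum change from baseline across all postoperative visits". Change is follow-up minus baseline (SAP 4.1.2), so the minimum is the worst observed change.

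SAP 4 gives the default for percentages, which applies unless stated otherwise: "subjects with missing visit data will be omitted from both the numerator and denominator of such calculations". SAP 7.1.3 adds that "Summaries for the overall study will include data from unscheduled visits".

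The cornea is also examined in another way. SAP 7.1.3.2 states: "Slit lamp measures collected on the CRF include corneal edema, corneal opacity, epithelium, endothelium, guttata" and further items, with edema and opacity recorded at Screening and every postoperative visit. SAP 5.6 tabulates ocular procedures in the study eye from the exchange date on.

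The visible text gives no rule for an image that cannot be graded. The SAP contents list names derivation rules only for visual acuity and IOP.

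**The concern.** The eyes most likely to lack a gradable image include those whose endothelium has done worst, because an edematous or decompensated cornea may not give a readable image. The missingness then depends on the outcome itself. The by-visit rule removes such an eye. The worst-visit rule cannot use a value that does not exist, so it falls back on an earlier one, and an eye that later failed can appear under little or no loss.

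This matters because the study's only objective is the safety of the exchange procedure and specular microscopy is a listed safety endpoint. No formal testing is planned, so the descriptive percentages are themselves the result. The table could show no endothelial loss in a study where a cornea had failed.

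**Working it through.** The documents state no expected ECD-loss rate and no expected number of ungradable images, so there is no plan figure to reproduce. The check applies the SAP rules to assumed counts.

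**Inputs**
- N = 45 study eyes, from the approximate number of subjects in Protocol 6.1, one eye each.
- x = eyes with a graded loss in the category of interest (assumed 0 to 2).
- k = eyes ungradable at Month 12 because of corneal failure (assumed 1 to 3).
- All other eyes are assumed to attend and to have gradable images.

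**Formulas**
- Month 12 row under SAP 4: x/(N − k).
- Overall row when each of the k eyes has an earlier, milder postoperative value: x/N.
- Overall row when the k eyes have no postoperative value at all: x/(N − k).
- Comparator that counts the failed corneas as loss: (x + k)/N.

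**Results for N = 45**

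| x | k | Month 12 row | Overall row, earlier milder value | Failed corneas counted |
|---|---|---|---|---|
| 0 | 1 | 0/44 = 0.0% | 0/45 = 0.0% | 1/45 = 2.2% |
| 0 | 3 | 0/42 = 0.0% | 0/45 = 0.0% | 3/45 = 6.7% |
| 1 | 1 | 1/44 = 2.3% | 1/45 = 2.2% | 2/45 = 4.4% |
| 2 | 2 | 2/43 = 4.7% | 2/45 = 4.4% | 4/45 = 8.9% |
| 2 | 3 | 2/42 = 4.8% | 2/45 = 4.4% | 5/45 = 11.1% |

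In the overall row the shortfall is (x + k)/N − x/N = k/N, or 1/45 = 2.2 percentage points per eye. In the Month 12 row it is the same when x = 0 and slightly smaller otherwise: for x = 2 and k = 2 it is 8.9 − 4.7 = 4.2 points, against 4.4 overall.

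**Which eyes are affected in the overall row**
- Gradable and milder at Month 3 or at an unscheduled visit, ungradable at Month 12: classified by the earlier value, so loss is understated.
- Never gradable after surgery: no value, so dropped, and loss is still understated.
- Already in the worst category at an earlier visit: stays there, and the overall row is right.

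For scale, the exact 95% interval is 0.0% to 7.9% for 0/45 and 0.1% to 11.8% for 1/45. One eye is small against sampling error, but this error runs in one direction.

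**The case against.** The strongest reply is that a failed cornea would not be lost from the report. It would appear in slit-lamp edema and opacity grades by visit, in central corneal thickness, in the count of eyes losing 15 or more letters, in the adverse event tables, and in concurrent procedures if the cornea were replaced. The ECD listing and the number of observations in the continuous summaries would also show that a value is missing. This stands, and it confines the problem to the ECD-loss table. However, none of these outputs is tied to that table, so its reader would have to match subjects across listings.

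Several stronger readings are tempting, and the documents do not support them:
- *That such an eye is always judged on Month 3 alone.* Unscheduled values enter overall summaries, so a worse unscheduled image would count.
- *That the worst outcome always lowers the percentage.* Dropping an eye shrinks the denominator: 2/43 = 4.7% is above 2/45 = 4.4%. The figure is low only against counting the failed cornea as a loss. A minimum over visits is also the cautious choice for eyes that do have values.
- *That the reason for a missing image is already recorded.* A slit-lamp grade shows edema or opacity at the same visit, not why the image failed. No visible text describes a gradability field.
- *That the SAP certainly has no rule.* The list of loss categories is not visible, and SAP 1 places table specifications in another document.
- *That every such eye should simply be scored as worst loss.* Opacity need not be endothelial and edema may be transient, so this does not belong in the main figure.

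The counts are assumed. Protocol 6.2.2 excludes some corneal disease at Screening (the wording is partly redacted), so there may be no such eye.

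**Conclusion.** The point holds as a reporting gap in one safety table. The stated rules in SAP 4 and 7.1.3.8 together take an eye with a failed cornea out of the Month 12 loss percentages. Overall, they classify it by an earlier value or drop it. Unless that earlier value was already in the worst category, the table understates loss relative to counting the eye, by about 2.2 percentage points per eye when N is about 45.

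The direction of that comparison follows from the rules. Its size rests on the assumed number of such eyes, which may be zero. The conclusion also assumes that the category list, which cannot be seen, makes no exception. It does not mean that the event is hidden from the study report, or that the overall row is wrong for every ungradable eye.

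**What to change.** In SAP 7.1.3.8, unless the category list already does so:
- At each specular visit and for the overall study, add a row counting eyes with no gradable image and either concurrent corneal edema or opacity (from the slit-lamp data) or a corneal replacement (from concurrent ocular procedures). Use all eyes examined as the denominator.
- Keep the gradable-only percentages as the main figures.
- Beside them, show a pre-specified worst-case version that places eyes ungradable with corneal edema or decompensation, or with a corneal replacement, in the highest loss category.

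The cost is one rule and a few table cells, built by linking data that the SAP already tabulates. No new examination is needed. The downside is small: the worst-case category is assigned and not measured, and that figure may look less favourable. Settling the rule before the single database lock avoids choosing it once an affected eye is known.
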